**For HIV-infected individuals:**

If 1 DLT occurs within 7 days of a subject receiving Trogarzo® via IM injection, then the DMC should be notified, and dosing of additional IM Group subjects may continue. However, the individual experiencing the DLT should resume dosing as per current FDA-approved administration instructions and the subject will discontinue from the study.

If 2 DLTs occur within 14 days of a subject receiving Trogarzo® via IM injection, then the DMC should be notified; however, dosing of additional IM Group subjects may continue. The individuals experiencing the DLT should resume dosing as per current FDA-approved administration instructions and the subjects will discontinue from the study.

If 3 DLTs occur within 14 days of a subject receiving Trogarzo® via IM injection, then the DMC should be notified, and further dosing of IM Group subjects should be suspended. All IM Group subjects should resume dosing as per current FDA-approved administration instructions.

Any SAE deemed related to study drug administration will result in cessation of dosing via IM injection. The DMC should review the event and all Trogarzo® dosing should resume as per current FDA-approved administration instructions to avoid loss of virologic control. The DMC will determine whether dosing by IM injection may resume in additional participants.

Refer to [Appendix C](#) for further information on the management of suspected anaphylactoid reactions. Study drug should only be administered in a setting that allows for rapid access to emergency cardiopulmonary support services in the event of a life-threatening infusion-related AE (e.g., anaphylaxis).

## 4.4 Study Stopping Rules

In consultation with the DMC:

- Any 2 DLTs in the Sentinel Group that the DMC confirms to be probably or definitely due to the administration of Trogarzo® at a faster rate or increased concentration or both
- Any 2 DLTs in the HIV-uninfected volunteers in the Core Group occurring within 7 days of treatment that the DMC confirms to be probably or definitely due to the administration of Trogarzo® by IVI, IV push, or IM will result in the discontinuation of enrollment of HIV-uninfected healthy volunteers. HIV-uninfected volunteers already enrolled in the study may complete the trial if they do not meet these DLT criteria.
- Any 3 DLTs in the Core IVP or IM Groups that the DMC confirms to be probably or definitely due to the administration of Trogarzo® at a faster rate or increased concentration or both
- Any SAE in any Group that the DMC confirms to be probably or definitely due to the administration of Trogarzo® at a faster rate or increased concentration or both

## 4.5 Study Drug Description

HIV-infected study participants will be treated with commercially packaged Trogarzo® according to the instructions for infusion in the approved prescribing information both prior to and after completion of this study. HIV-uninfected healthy volunteers will be treated with drug packaged and labeled for clinical research use provided to study sites by the study sponsor.

To prevent potential loss of benefits and disruption of drug availability to the HIV-infected participants, study drug will be obtained at the clinical sites using the same means for obtaining the commercial drug employed for that subject prior to study entry and after study completion. Thus, investigators will be asked to apply labels to the TMB-302 study drug as required for an Investigational New Drug Application (IND) study utilizing labels and procedures provided by the Sponsor or Designee.

Trogarzo® is a single-use parenteral formulation contained in a 2 mL, clear-glass vial, and packaged into cartons containing 2 vials each. The drug product contains ibalizumab-uiyk at a concentration of 150 mg/mL, histidine United States Pharmacopoeia (USP), sucrose, sodium chloride, polysorbate 80, and water for injection USP at pH 6.0. Each vial contains at least 1.33~ mL of fluid delivering a

total of 200 mg study drug per vial. Each 800 mg dose of study drug will thus require 4 vials (2 cartons for HIV-infected and 4 cartons for HIV-uninfected due to differences in packaging) of Trogarzo®. The stability of Trogarzo® at 2°C to 8°C is evaluated in ongoing studies. For any period of storage, Trogarzo® must be under refrigerated conditions with a temperature-monitoring device. Trogarzo® should be maintained at 2°C to 8°C (but NOT FROZEN) and protected from light in accordance with Trogarzo® packaging information.

Any spent vials or remaining contents of used vials should be destroyed according to the site's procedures for spent vial destruction and disposal only after complete drug accountability records have been reviewed and accepted during routine monitoring, and written permission has been given for spent vial destruction. The destruction should be documented.

## **4.6 Study Drug Accountability**

The investigator will maintain accurate records of all study drug, including when, how much, and condition under which the study drug is received, dispensed, and destroyed by site personnel. In addition, the administration of study drug to each subject should be documented to the vial level for each infusion (i.e., lot number of every vial for that infusion, expiration date, time of infusion preparation, time and duration of administration, and documentation of full infusion received). Reasons for deviation from the expected dispensing regimen must also be recorded. Drug accountability will be reviewed and documented at each study monitoring visit. Reconciliation and accountability of study drug will be done throughout the study during the monitoring visits. The Sponsor or designee shall maintain written records of all drug dispositions, which will include the name of the investigator, the date, quantity, batch or code of each such shipment, and method of disposal. Disposal may only occur after complete drug accountability records have been reviewed and accepted during routine monitoring, and written permission has been given for used vial destruction.

## **5. Subject Enrollment**

Approximately 40 subjects will be enrolled into the study at approximately 7-8 sites in the United States. Approximately twenty subjects will receive Trogarzo® via an IV push and approximately 20 subjects will receive Trogarzo® via IM injection. Subjects will be enrolled only if they meet all of the inclusion criteria and none of the exclusion criteria.

## 5.1 Inclusion Criteria

### HIV-infected participants:

Subjects must meet all of the following criteria to be included in the study:

1. Are capable of understanding and have voluntarily signed the informed consent document
2. Currently receiving a stable Trogarzo®-containing ARV regimen for a minimum of 3 months, and no change in background ARVs anticipated over the period of study participation; a stable regimen is defined as having no changes in dose or frequency and no interruptions  $\geq 2$  weeks during the 3-month period
  - Note: For subjects who receive Trogarzo® as an IV push (Core Group) and then enter the study to receive Trogarzo® as an IM injection (IM Group), the period while receiving the IV push will be considered as having received a stable Trogarzo®-containing ARV regimen.
  - Note: HIV-infected subjects who are enrolled in the IM injection study and are unable to adhere to the study schedule for IM dosing due to factors outside the study will be discontinued. Re-enrollment of HIV-infected IM Group subjects will be allowed after a Discontinuation Visit and Screening Visit are completed provided that inclusion/exclusion criteria continue to be satisfied and dosing after discontinuation is resumed according to the Trogarzo® Prescribing Information. For re-enrolling subjects, the inclusion criteria for stable a Trogarzo®-containing ARV regimen is satisfied with a loading dose of 2000mg IVI and at least one maintenance dose of 800mg IVI given according to Trogarzo® labeling prior to Day 1 enrollment.
3. Have no AIDS-defining events in the 3 months before Screening, other than cutaneous Kaposi's sarcoma or wasting syndrome due to HIV.
4. Are able and willing to comply with all protocol requirements and procedures
5. Are 18 years of age or older
6. Have a life expectancy that is  $>6$  months
7. Have a viral load  $<1,000$  copies/mL at Screening
8. CD4 $^{+}$  T-cell count  $>50$  cells/mm $^{3}$  at Screening

---

- 9. Prothrombin time (PT) and partial thromboplastin time (PTT) <1.5 times the upper limit of normal (IM Group only)

**HIV-uninfected individuals:**

- 1. Healthy volunteers born male and female as assessed by medical history and physical examination
- 2. Aged  $\geq 18$  and  $\leq 50$  years at the time of Screening
- 3. Ability and willingness to provide written informed consent
- 4. Willingness to comply with protocol schedule
- 5. Willingness to undergo HIV-1 testing
- 6. Non-reactive 4th generation point of care HIV-1 test at Screening
- 7. Hepatitis B Surface antigen negative
- 8. Hepatitis C antibody negative, or if reactive, Hepatitis C RNA undetectable in plasma
- 9. PT and PTT <1.5 times the upper limit of normal (IM Group only)
- 10. Volunteers born female of reproductive potential who are sexually active with a male sex partner must agree to use one effective method of contraception from the time of signing the consent to completion of the study and agree to pregnancy testing as per the schedule of events.

Volunteers born female with reproductive potential are defined as pre-menopausal volunteers born female who have not had a sterilization procedure (e.g., hysterectomy, bilateral oophorectomy, tubal ligation or salpingectomy). Volunteers born female are considered menopausal if they have not had a menses for at least 12 months and have a follicle-stimulating hormone (FSH) of greater than 40 IU/L or if FSH testing is not available, they have had amenorrhea for 24 consecutive months.

## **5.2      Exclusion Criteria**

**HIV-infected participants:**

Subjects having or meeting any of the following conditions or characteristics will be excluded from the study:

1. Any active AIDS-defining illness according to the Centers for Disease Control and Prevention (CDC) Revised Surveillance Case Definitions for HIV Infection 2008 (Morbidity and Mortality Weekly Report (MMWR) Vol.57/No. RR-10, [Appendix A](#)), or history of the same during the 3 months preceding Screening, with the following exceptions: cutaneous Kaposi's sarcoma and wasting syndrome due to HIV
2. Any significant diseases (other than HIV-1 infection) or clinically significant findings, including psychiatric and behavioral problems, determined from Screening, medical history, and/or physical examination that, in the investigator's opinion, would preclude the subject from participating in this study
3. Any significant acute illness within 1 week before the initial administration of study drug
4. Any active infection secondary to HIV requiring acute therapy; however, subjects that require maintenance therapy (i.e., secondary prophylaxis for opportunistic infections) will be eligible for the study
5. Any immunomodulating therapy (including interferon), systemic steroids, or systemic chemotherapy within 12 weeks before Enrollment
6. Any vaccination within 7 days before Day 1
7. Any female subject who either is pregnant, intends to become pregnant, or is currently breastfeeding
8. Any current alcohol or illicit drug use that, in the investigator's opinion, will interfere with the subject's ability to comply with the study schedule and protocol evaluations
9. Any radiation therapy during the 28 days before first administration of study medication
10. Any Grade 3 or 4 laboratory abnormality according to the Division of AIDS (DAIDS) grading scale, except for the following asymptomatic Grade 3 events:
  - triglyceride elevation
  - total cholesterol elevation
  - or Grade 3 or 4 reductions in levels of CD4+ T cells
11. History of coagulopathy that would preclude administration of IM injections (IM Group only)
12. Skin rashes or tattoos that would prevent ability to assess IM injection for injection-site reactions (IM Group only)
13. Use of high-dose aspirin, clopidogrel, prasugrel, ticagrelor, dipyridamole or other antiplatelet medication that would interfere with the ability to receive IM injections (IM Group only).

#### **HIV-uninfected individuals**

1. Confirmed HIV-1 infection
2. At high risk of severe COVID-19 disease as defined by one of the following:
  - History of hypertension, atherosclerotic cardiovascular disease (ASCVD), coronary artery disease, diabetes mellitus
  - History of asthma or chronic pulmonary disease
  - History of renal disease and chronic renal insufficiency
  - BMI over 35
3. Any acute or chronic medical condition that in the opinion of the investigator would preclude participation
4. Chronic autoimmune disease
5. Active IV drug use
6. Excessive use of alcohol or recreational drugs that in the opinion of the investigator would preclude participation
7. Decompensated psychiatric illness
8. Need for chronic immunotherapy including systemic corticosteroids, other MAb therapy, or immunosuppressive drugs
9. Volunteers born female who are pregnant, lactating, or planning on becoming pregnant over the study period
10. Any of the following laboratory parameters:
  - Hemoglobin <10.0 g/dL
  - Absolute neutrophil count <1,000/mm^3
  - Absolute lymphocyte count <500/mm^3
  - Platelet count <100,000/mm^3
  - Creatinine >1.25x upper limit of normal (ULN)
  - Aspartate aminotransferase (AST) >1.5x ULN
  - Alanine aminotransferase (ALT) >1.5x ULN
  - Glucose (non-fasting) >160 mg/dL
  - Proteinuria: 2+ or greater
  - Hematuria: >10 red blood cells (RBCs) per high-power field

11. Previous receipt of an experimental MAb for HIV-1 treatment or prevention in a research study
12. History of severe allergic reactions to drugs, vaccines, or drug infusion
13. Participation in another investigational clinical trial within the past 12 weeks or anticipated during the course of the current study
14. History of coagulopathy that would preclude administration of IM injections (IM Group only)
15. Skin rashes or tattoos that would prevent ability to assess IM injection for injection-site reactions (IM Group only)
16. Use of high-dose aspirin, clopidogrel, prasugrel, ticagrelor, dipyridamole or any other antiplatelet medication that would interfere with the ability to receive IM injections (IM Group only).

## 5.3 Subject Withdrawal and Discontinuation

### 5.3.1 Reasons for Withdrawal or Discontinuation

A subject may be withdrawn or discontinued from the study if:

- The subject withdraws consent to participate or requests an early discontinuation at any time during the study
- The subject is in violation of the protocol
- The subject becomes pregnant during the study ([Section 8.7](#) for a description of procedures to be followed in case of pregnancy)
- The subject experiences a severe drug-related AE during study drug administration or during the post-administration observation period
- Upon determination by the investigator that withdrawal from the study is in the best interests of the subject
- Any HIV-uninfected subject in the Core Group who tests positive for HIV-1 during the course of the study will be withdrawn.
- Refer to Sections 6.1, 6.2, and 6.3 for additional reasons for study discontinuation

Refer to [Sections 4.3](#) and [4.4](#) for detailed information on the Safety Monitoring and Toxicity Management Plan and the Study Stopping Rules.

A subject experiencing one or more treatment-emergent SAEs will receive treatment and follow-up evaluations by the investigator, or they will be referred to another appropriate physician for treatment and follow-up. Withdrawal from the study will be at the discretion of the investigator/Sponsor.

The investigator will also withdraw a subject upon the request of the DMC ([Section 8.8](#)) or if the Sponsor or local regulatory agency (e.g., FDA) terminates the study. Upon occurrence of an SAE, the Investigator will notify the Sponsor or designee via the SAE hotline of these events ([Section 8.6](#)). If a subject is discontinued because of an AE, the event will be followed until satisfactory resolution or until the investigator deems the event to be chronic or the subject to be stable.

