Other therapies designed to prevent infection of host cells (i.e., entry inhibitors) are currently approved for treatment of HIV infection in treatment-experienced subjects. Fuzeon® (enfuvirtide, T-20), a fusion inhibitor and SelzentryTM (maraviroc), a coreceptor antagonist have both been shown

to be efficacious when combined with an OBR in treatment-experienced subjects. Trogarzo®, a MAb, is a cluster of differentiation 4 (CD4)-directed post-attachment inhibitor that also blocks HIV entry and is approved for use in combination with other approved antiretroviral (ARV) medications in treatment-experienced subjects with multi-class resistant HIV-1.

Clinical trials conducted with IV Trogarzo® to assess safety and efficacy are described in the sections that follow. The safety data from two small studies with subcutaneous (SC) and IM administration are also discussed.

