An additional group of approximately 20 subjects (the IM Group), which will include subjects receiving Trogarzo® as an IM injection, will also be evaluated. Subjects who have previously received Trogarzo® as an IV push are permitted to screen/enroll for participation in the IM Group. Subjects for inclusion in the IM Group who were part of Sentinel or Core Groups will enter the IM Group only once they have completed the Sentinel or Core study. New subjects enrolled in the IM Group who were not part of the Sentinel or Core Groups will be recruited only once all Core Group subjects have been enrolled and completed the Core study. These subjects may be HIV-infected or -uninfected.

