**For HIV-uninfected healthy volunteers:**

If 1 DLT occurs within 7 days of a subject receiving Trogarzo® by IVI or IV push over 30 seconds, then the DMC should be notified, and dosing of additional Core Group subjects may continue. However, the individual experiencing the DLT should discontinue dosing and be observed for 28 days prior to study discontinuation.

If 2 DLTs occur within 7 days of a subject receiving Trogarzo® by IVI or by IV push over 30 seconds, then the DMC should be notified; however, dosing of additional HIV-1 infected Core Group subjects may continue. The individuals experiencing the DLT should discontinue dosing and be observed for 28 days prior to study discontinuation. The DMC should at this point review.

If 3 DLTs occur within 7 days of a subject receiving Trogarzo® by IVI or IV push over 30 seconds, then the DMC should be notified, and further dosing of Core Group subjects should be suspended. All Core Group subjects should resume dosing as per current FDA-approved administration instructions.

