**For HIV-uninfected healthy volunteers:**

If 1 DLT occurs within 7 days of a subject receiving Trogarzo® by IVI or IM injection, then the DMC should be notified, and dosing of additional IM Group subjects may continue. However, the individual experiencing the DLT should discontinue dosing and be observed for 28 days prior to study discontinuation.

If 2 DLTs occur within 7 days of a subject receiving Trogarzo® by IVI or by IM injection then the DMC should be notified; however, dosing of additional HIV-1 uninfected IM Group subjects may continue. The individuals experiencing the DLT should discontinue dosing and be observed for 28 days prior to study discontinuation. The DMC should at this point review.

If 3 DLTs occur within 7 days of a subject receiving Trogarzo® by IVI or by IM injection, then the DMC should be notified, and further dosing of IM Group subjects should be suspended. All IM Group subjects should resume dosing as per current FDA-approved administration instructions.

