### **7.2.10    4th Generation Point of Care HIV-1 Testing**

All HIV-1 uninfected healthy subjects will be tested at Screening and Day -55 and during the course of the study as outlined in [Table 2](#), Table 3, and Table 4 with a 4th generation point of care HIV test using blood collected at the visit. If a test is reactive, then blood should be sent to the Central lab for confirmatory HIV-1 testing which includes testing for HIV-1 by nucleic acid amplification (NAAT) and a serologic response to HIV-1 (Geenius HIV1/2 Biorad).

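### Volunteer safety rules were not fully extended to the IM Group: withdrawal on a positive HIV test and the 2-DLT enrollment stop name only Core volunteers, and the 3-DLT action does not fit volunteers

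*Protocol*

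**What the plan says.** **Positive HIV test.** Protocol 5.3.1 states: "Any HIV-uninfected subject in the Core Group who tests positive for HIV-1 during the course of the study will be withdrawn". Protocol 7.2.10 states: "All HIV-1 uninfected healthy subjects will be tested at Screening and Day -55 and during the course of the study", and refers to Table 4, the IM schedule, as well as Tables 2 and 3.

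**Two DLTs.** Protocol 4.4, second bullet, is triggered by "Any 2 DLTs in the HIV-uninfected volunteers in the Core Group occurring within 7 days of treatment" that the DMC attributes to dosing by IVI, IV push or IM. Its consequence is to end enrollment of healthy volunteers. It adds: "HIV-uninfected volunteers already enrolled in the study may complete the trial if they do not meet these DLT criteria". Protocol 3.1 says that new IM subjects "will be recruited only once all Core Group subjects have been enrolled and completed the Core study". At the second volunteer DLT, Protocol 4.3 calls for DMC notification and review in both groups. It then says for Core that "dosing of additional HIV-1 infected Core Group subjects may continue" and for IM that "dosing of additional HIV-1 uninfected IM Group subjects may continue".

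**Three DLTs.** For volunteers, 4.3 counts DLTs within 7 days of IVI or of the test route. It suspends further dosing in the group and directs all of that group's subjects to resume approved administration. Protocol 3.3 identifies this as the diluted 15-minute infusion.

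**Related SAE.** In 4.3 the paragraphs halting push or IM dosing after a related SAE are worded for any such event, but they are printed under the HIV-infected headings. They justify the return to approved dosing by the need to keep virologic control.

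**The concern.** The IM portion arrived with Amendment 5 (IM SAP, Section 1). The text looks as though IM was added to the list of routes while the groups named in some volunteer rules stayed as they were. That history is an inference; the gaps in the current text are not.

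Healthy volunteers bear risk without therapeutic benefit, so their group-level rules should not depend on interpretation. Three things are at stake:

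- An IM volunteer who becomes infected could go on receiving a drug that Protocol 1.1 describes as "approved for use in combination with other approved antiretroviral (ARV) medications in treatment-experienced subjects with multi-class resistant HIV-1". Unless treatment were started, that volunteer would be receiving it alone.
- Two DLTs among new IM volunteers would not close volunteer enrollment, as two in Core would.
- After three volunteer DLTs, the unaffected volunteers are directed to a route on which some or all of those DLTs may have occurred.

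**Working it through.** The plan gives no operating characteristics for these rules, so there is no figure to reproduce. The check compares the texts and counts doses.

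**1. Doses left after each HIV test in an IM volunteer.** Dosing days (Protocol 3.1) are -55, -41, -27, -13, 1, 15 by IVI and 29, 43, 57, 71 by IM. Point-of-care tests after the first dose are on Day -27 (Table 2) and on six visits in Table 4. The Table 4 columns are broken in the text available; aligning that row with the hematology row gives Days 1, 29, 43, 57, 71 and 99. Later doses exclude the dose on the test day itself.

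| Test day | Later doses | mg (800 each) |
|---|---|---|
| -27 | 7 | 5,600 |
| 1 | 5 | 4,000 |
| 29 | 3 | 2,400 |
| 43 | 2 | 1,600 |
| 57 | 1 | 800 |
| 71 | 0 | 0 |
| 99 | 0 | 0 |

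Five of seven tests leave at least one dose that mandatory withdrawal would prevent. The first exclusion criterion for volunteers does not fill the gap: it governs entry, and Table 2 schedules the criteria review only at Screening and Day -55.

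**2. The DLT ladder for volunteers.**

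| DLTs | Core volunteers | New IM volunteers |
|---|---|---|
| 1 (4.3) | DMC notified; that volunteer stops, observed 28 days | Same |
| 2 (4.3) | DMC notified and reviews; HIV-infected subjects may continue | DMC notified and reviews; HIV-uninfected subjects may continue |
| 2 (4.4) | Volunteer enrollment stops | Not named |
| 3 (4.3) | Dosing suspended; all resume approved dosing | Same |

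New IM subjects start only after Core has finished, so their DLTs fall outside a count of volunteers in the Core Group.

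As an illustration only, let n be the number of new IM volunteers and p the chance that each has a DLT that counts. The documents give neither; n could be anything from 0 to about 20. With independent volunteers, P(2 or more) = 1 − (1−p)^n − np(1−p)^(n−1). For n = 10, p = 5%: 1 − 0.5987 − 0.3151 = 8.6%.

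| n | p | 2 or more | exactly 2 | 3 or more |
|---|---|---|---|---|
| 10 | 2% | 1.6% | 1.5% | 0.1% |
| 10 | 5% | 8.6% | 7.5% | 1.2% |
| 10 | 10% | 26.4% | 19.4% | 7.0% |
| 20 | 2% | 6.0% | 5.3% | 0.7% |
| 20 | 5% | 26.4% | 18.9% | 7.5% |
| 20 | 10% | 60.8% | 28.5% | 32.3% |

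The "2 or more" column shows how often the missing stop would act. The "exactly 2" column shows how often the count would never reach the 3-DLT suspension.

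**3. Fit of the 3-DLT action.** Volunteer IVI doses: 2,000 + 5 × 800 = 6,000 mg in 6 doses. Test-route doses: 4 × 800 = 3,200 mg in 4 doses. So 6 of 10 doses (6,000 of 9,200 mg) are IVI, and the trigger counts DLTs on them. The action then directs everyone to IVI, although volunteers stop after Day 71 by design and have no virologic control to protect. The 4.4 stops at 3 DLTs and for SAEs require attribution to a faster rate or increased concentration, so events on standard IVI fall outside them.

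**The case against.** The other side has real points, and several limit what can be claimed.

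- **Rollover.** A reader might infer that no DLT on IM can ever count toward the 4.4 enrollment stop. The documents do not support that. Core completers may enter the IM Group (Synopsis; 3.1), so a Core volunteer can receive all three listed routes, and a rolled-over volunteer's DLTs may count. The gap is established only for new IM volunteers.
- **DMC review.** A reader might infer that nothing happens at group level between the first and third DLT. In fact 4.3 requires DMC review at the second, and under 8.8 the DMC may recommend modification or termination.
- **Who goes back to infusion.** A reader might infer that volunteers with a DLT are re-exposed. They have already stopped dosing, and the 3-DLT rule suspends dosing first. Only the remaining volunteers are affected.
- **Related SAEs.** A reader might infer that these paragraphs exclude volunteers. Their position under the HIV-infected headings and the virologic rationale point that way. However, they are worded for any related SAE, and the IM paragraph is followed, under the same heading, by emergency-support requirements that cannot sensibly be limited to infected subjects. The scope is ambiguous.
- **Design choice.** Aiming halts at the experimental routes rather than the approved infusion is defensible. The documents do not show that one related SAE on IVI must halt all volunteer dosing.

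Discretion also exists: 5.3.1 and 5.3.2 let investigators withdraw anyone, reactive tests go to confirmation, and the DMC can request withdrawal. These points reduce the impact. They do not explain why Core volunteers have a mandatory rule and IM volunteers do not, or why the two 2-DLT paragraphs name opposite populations.

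**Conclusion.** The point holds as an inconsistency that should be fixed, with limited practical impact.

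- Mandatory withdrawal on a positive HIV test is missing for IM volunteers and rests on discretion. Five of seven tests leave 1 to 7 later doses. This count relies on the reading of Table 4; the gap itself does not.
- For new IM volunteers, the 2-DLT enrollment stop does not apply, and the next written DLT stop comes at 3. The probabilities above rest on assumed DLT rates and numbers, and the conclusion does not depend on them.
- In both groups the 3-DLT action does not fit the remaining volunteers. The figure of 6 in 10 doses measures exposure to IVI, not risk.
- The reach of the related-SAE paragraphs to volunteers is unclear and needs a sentence, not a new rule.

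**What to change.** 1. **5.3.1:** make withdrawal mandatory for every HIV-uninfected subject, in the Core or the IM Group, whose positive HIV-1 test is confirmed.
2. **4.4, second bullet:** name HIV-uninfected volunteers in the Core or IM Group, and say whether the two groups are counted together or separately. Align both 2-DLT volunteer paragraphs in 4.3 with it: volunteer enrollment stops, while HIV-infected subjects and unaffected volunteers already enrolled may continue.
3. **4.3, volunteer 3-DLT paragraphs:** HIV-infected subjects resume approved IVI; volunteers stop dosing pending DMC review.
4. **4.3, related-SAE paragraphs:** state that they apply to all subjects in the group, and that the instruction to resume approved dosing applies to HIV-infected subjects only.

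This is a wording amendment with no new visits or tests. With a separate count per group, IM volunteer enrollment could stop one DLT earlier (at 2 rather than 3). Some volunteers could miss doses during DMC review, which would disturb the steady state that the lead-in builds for the PK comparison. Because 5.3.2 allows replacement only for reasons other than safety under 4.3, the amendment should also say whether volunteers lost to such a pause may be replaced.
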